there is also a question whether the non- affected hemisphere may interfere with the process of recovery. It is currently not known what factors influence the activity of non- affected hemisphere to either support or interfere with the recovery of stroke. A better understanding of those events is critical to development of optimal therapeutic strategies. For example, non-invasive stimulation of specific areas of the non- affected hemisphere may help to improve functional recovery following stroke. The objectives in this application are to define the factors that influence the activity in the non- affected hemisphere to either support or interfere with the recovery after stroke. We will study the area of the brain that controls movements called motor cortex of the non- affected hemisphere (non- affected motor cortex) as it relates to motor function post-stroke.

In a longitudinal study of stroke patients, non- affected motor cortex reorganization will be assessed in two Specific Aims. In the first Specific Aim, we will determine the extent of functional and structural non- affected motor cortex reorganization using complementary techniques of transcranial magnetic stimulation (TMS), functional and structural MRI of the brain. In the second Specific Aim, the contribution of non- affected motor cortex reorganization to the recovery of motor function will be studied. Repetitive TMS will be used to transiently disrupt non- affected motor cortex function, thereby determine its role for the motor performance of the paretic limb. rTMS related improvement of motor performance would identify a supportive role of contralesional M1 while deterioration of motor performance would indicate its detrimental role. Different rTMS protocols will be applied to non- affected motor cortex to determine

whether non- affected motor cortex can be primed to enhance restorative therapy.

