### 3. Objectives:

**A. Specific Aim #1: *Define key factors that determine the reorganization of contralesional M1 during post stroke recovery process by comparing M1 excitability of stroke patients to that of healthy subjects.*** Our working hypothesis is that the extent of M1 and/or corticospinal tract (CST) damage, as measured by the electromyographic response to TMS of lesioned M1, stroke lesion volume, increased fractional anisotropy (FA) asymmetry of the CST, and quality of wrist/finger extension movements, will determine the extent of contralesional M1 reorganization. In a subset of patients we will also use electroencephalography and TMS to determine the additional key factor of connectivity between the lesioned and the non- lesioned M1 in the post- stroke reorganizational process of contralesional M1.

**B. Specific Aim #2: *Determine the role of contralesional M1 in motor performance during the post stroke recovery process.*** Our working hypothesis is that, during recovery, contralesional M1 contributes to improved motor performance and recovery of the paretic hand in patients with larger M1 and/ or CST damage. Specifically, the extent of M1 and/or CST damage as measured by the electromyographic response to TMS of lesioned M1, lesion volume, increased FA asymmetry of the CST, and quality of wrist/finger extension movements(Nijland et al. 2010) will determine whether contralesional M1 plays a supportive or detrimental role in post-stroke recovery process.

At the completion of this project, we expect to have identified the extent to which

contralesional M1 reorganization determines motor performance during the different phases of post-stroke recovery and can be targeted by interventions depending on its “state” (role) in the recovery process. This latter knowledge would be expected to have a substantial positive impact on treatment for stroke patients as it will provide crucial evidence to develop evidence based TMS treatment protocols that are tailored to the state of therapeutic target. The clinically important question of whether decreasing contralesional M1 activity in patients post stroke is always helpful or at times is detrimental will be addressed.

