#### **4.4. Studies pertaining to Specific Aim #2: *Determine the role of contralesional M1 in motor performance during the post stroke recovery process***

In two studies (Study 1 and 2) we will test the effect of contralesional M1 transcranial magnetic stimulation on the subject's performance in a manual pointing task (4 different level of complexity, Presentation®) using either the paretic or the non-paretic hand in a counterbalanced randomized order and measures of motor excitability (IHI, SICI, MT, SRC, see above for details). To accomplish the goal of each study, a total of 6 experiments will be conducted in a randomized counterbalanced order. In Study 3 we will implement prediction and classification models to determine the predictive roles of variables measured in specific aim 1 on the supportive/detrimental role of cl\_M1 derived

from the effect of M1 downregulation by rTMS (Specific aim 2, study#1).

Study #1: Role of cl\_M1 on motor performance. In all subjects, we will test the effect of 1 Hz rTMS and sham cl\_M1 stimulation on the subject's performance in a pointing task of increasing difficulty using either the paretic or the non-paretic hand in a counterbalanced randomized order. Specifically, as previously described by our group in detail (Butefisch et al. 2003; Butefisch et al. 2008) rTMS at 90% MT will be used to decrease cl\_M1 function using a rapid Magstim (Magstim Company, UK). Briefly, coil position will be monitored online using Brainsight. EMG activity will be recorded from the ECU and other control muscles with the settings already detailed in Specific Aim 1. After determining the MT in the ECU hot spot (Rossini et al. 1994b), rTMS will be applied through the air-cooled figure-of-eight coil at 90% MT and 1 Hz frequency for 15 min (Butefisch et al. 2009). The effects will be compared to Sham stimulation applied at similar intensity and frequency (Butefisch et al. 2009). An additional two visits will be conducted for healthy subjects that include a repeat of the study measures described in specific aim 1 but we will stimulate at 80% rTMS to explore the effects compared to 90% rTMS and these visits will take the standard amount of time of 2-3 hours per visit. Preliminary data demonstrated different effects of different intensities and this needs to be confirmed in this population.

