Study #2: Effect of transient disruption of cl\_M1 on M1 excitability and IHI. In all subjects, we will test the effect of cl\_M1 stimulation on the outcomes of MT, SRC, SICE and IHI in both motor cortices one month post stroke. All measurement will be repeated 6

months after infarction. The data will be compared to the results of healthy age matched controls to establish abnormality.

*Statistical analysis:* The statistical tests performed in this section will mirror those in the specific aim 1 with the addition of repeated measures factors specifying acquisition time (pre- or post-rTMS stimulation) and time post-stroke (1 and 6 months). The mixed-models will investigate the effect of cl\_M1 stimulation on TMS outcomes MT, SRC, SICE, rHI over time post-stroke. Additionally, we will use the mixed model to assess the effects of cl\_M1 excitability (SICE from SA #1) and cl\_M1 activation (number of activated voxels and % signal change within ROI) on rTMS-related changes in TMS measures.

Study #3: Identify biomarkers in the subacute and chronic phase of stroke that predict either the supportive or detrimental role of contralesional M1 as determined by responses to specific intervention protocols. In this study, we will implement prediction and classification models to determine the predictive roles of variables in SA #1 on the supportive/detrimental role of cl\_M1 derived from the effect of M1 downregulation by rTMS (SA#2, study#1). Specifically, we will train (and test) a binary classifier to predict subjects' responses (positive or negative) to rTMS (down regulation and sham) at 1 and 6 months post-stroke based on sets of predictors defined by SAs # 1 & 2. The association between the set of predictors and the binary response will be established during an iterative cross-validation process involving training and testing, in which different data are used to establish a predictive model and to evaluate its performance. We will assess performance using standard measures of prediction accuracy such as sensitivity,

specificity, positive predictive value, and negative predictive value. We will employ and compare multiple modeling techniques such as the Elastic Net, logistic classifier, and Bayes classifiers. Developing and optimizing the classifiers will identify subsets of measures that have the greatest predictive power for forecasting the role of cl\_M1.

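### Section 2's rule for calling contralesional M1 supportive or detrimental contradicts its own premise and the Aim 2 hypothesis, and Study 3 does not correct it

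*Combined protocol and SAP*

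**What the plan says.** Section 2 gives the premise for Aim 2: "Repetitive TMS will be used to transiently disrupt non- affected motor cortex function". The next sentence sets the interpretation: "rTMS related improvement of motor performance would identify a supportive role of contralesional M1 while deterioration of motor performance would indicate its detrimental role".

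Section 3 states the Aim 2 working hypothesis that, during recovery, "contralesional M1 contributes to improved motor performance and recovery of the paretic hand in patients with larger M1 and/ or CST damage". Its closing paragraph leaves open whether lowering contralesional M1 activity always helps or sometimes harms.

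In Section 4.4, Study 1 applies 1 Hz rTMS at 90% of motor threshold in order to lower contralesional M1 function, with sham as the comparator. Study 3 takes the supportive/detrimental class from the effect of that downregulation.

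- **Predictors.** The overview in Section 4.4 says Study 3 will "determine the predictive roles of variables measured in specific aim 1 on the supportive/detrimental role of" contralesional M1, and the Study 3 paragraph says nearly the same ("determine the predictive roles of variables in SA #1 on the supportive/detrimental role of" that area). The target of the classifier itself is written as "responses (positive or negative) to rTMS (down regulation and sham) at 1 and 6 months post-stroke based on sets of predictors defined by SAs", and both aims are named there.
- **Validation.** The plan describes cross-validation "in which different data are used to establish a predictive model and to evaluate its performance". It continues: "We will employ and compare multiple modeling techniques such as the Elastic Net, logistic classifier, and Bayes classifiers". It then expects that optimising the classifiers will reveal the most predictive subsets of measures.

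Section 6 only refers back to these sections, so nothing elsewhere settles the points below.

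**The concern.** The supportive/detrimental class is the outcome that Study 3 tries to predict, and Section 3 says the result should inform treatment matched to the state of contralesional M1. A class whose direction is wrong or unstated therefore affects the main message. An analyst who follows Section 2 literally would put each patient in the class opposite to the one Section 3 implies.

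A second, smaller risk concerns the reported accuracy. If several techniques are compared on the same folds that supply the accuracy estimate, and the winner is reported, the estimate is too high even when no predictor carries information.

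**Working it through.** The plan states no accuracy, power or patient number for Study 3, so there is no figure to reproduce. The direction question is settled by setting the text side by side. The numbers in steps 2 and 3 are illustrations under stated assumptions.

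**1. Direction.** The inputs are the premise and labelling sentence in Section 2, the hypothesis in Section 3, and the purpose of the 1 Hz stimulation in Section 4.4, Study 1.

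| What contralesional M1 does for the paretic hand | Expected change after downregulation | Class by Section 2's sentence | Class implied by Section 3 |
|---|---|---|---|
| Helps | Worse | Detrimental | Supportive |
| Interferes | Better | Supportive | Detrimental |

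The last two columns disagree in both rows. Suppose the Section 3 hypothesis is true. Patients with larger damage then get worse after downregulation, Section 2 calls their M1 detrimental, and the report says the hypothesis failed. The last column is an inference from the hypothesis plus suppressive stimulation; Section 3 does not write it as a rule. Study 3 never links positive or negative to either class.

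**2. What reversing the names does to the reported measures.** Assume 100 patients, 40 of them supportive, with sensitivity 80% and specificity 60%. The cells are TP = 32, FN = 8, FP = 24, TN = 36.

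- Names as assumed: sensitivity 32/40 = 80%, specificity 36/60 = 60%, PPV 32/56 = 57%, NPV 36/44 = 82%, accuracy (32 + 36)/100 = 68%.
- Names reversed: sensitivity 36/60 = 60%, specificity 32/40 = 80%, PPV 36/44 = 82%, NPV 32/56 = 57%, accuracy 68%.

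Accuracy is unchanged. Each named measure swaps with its partner.

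**3. Choosing the technique on the test folds.** This is a null simulation in which predictors are unrelated to the response, so true accuracy is 50%. Assumptions: 20, 30 or 60 patients, balanced classes, 20 independent predictors, one visit per patient, 5-fold stratified cross-validation, 400 runs. The techniques are elastic-net logistic, near-unpenalised logistic and Gaussian naive Bayes.

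| Procedure | N = 20 | N = 30 | N = 60 |
|---|---|---|---|
| One logistic model chosen in advance | 50.3% | 50.5% | 49.7% |
| Best of three, picked on the same folds | 57.1% | 56.9% | 54.4% |
| Selection in an inner loop | 48.8% | 49.7% | 49.4% |

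The inner-loop row selects among five candidates, because the elastic net enters at three penalties. A separate run of 150 replicates gave 57%, 58% and 56% for best of three with 20 predictors, and 58%, 55% and 54% with four. The excess over 50% is therefore about 4 to 8 percentage points.

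**The case against.** **Direction.** Section 2 is introductory text, and the sentence looks like a slip. Section 4.4 says only that the role is derived from the effect of downregulation, and the closing question in Section 3 points to the conventional reading. A careful analyst would probably label the classes that way. This is fair as to cause, but it does not remove the problem: the slip is the only explicit rule in the plan, and Study 3 neither corrects nor replaces it.

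**Selection.** The plan does promise different data for building and for evaluating a model. Choosing measures can be read as part of building, and the elastic net selects within its own fit. Comparing techniques is also not the same as reporting only the best. This stands in large part. What remains is that the choice among techniques, and their optimisation, is not placed inside the training data.

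**Predictors.** A reader might infer that the predictor set widens from Aim 1 to Aim 2 between sentences, so that a measurement used to form the label could also predict it. The documents do not support that as a demonstrated inconsistency. Section 3 names the same four predictors under both aims: the muscle response to TMS of the lesioned M1, lesion volume, FA asymmetry of the corticospinal tract, and quality of wrist and finger extension. The reference to both aims can mean that shared list. No section proposes a baseline or sham-session pointing score as a predictor. The wording is ambiguous, and that is all. The boundary between the aims would not be a safeguard in any case, because Aim 1 itself includes movement kinematics (Section 4.1) and a pointing task (Section 4.1.4).

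**Conclusion.** The labelling sentence in Section 2 is wrong as written. It contradicts the sentence before it and the Aim 2 hypothesis, and if followed it reverses the biological conclusion of Study 3. This rests on the text and on one premise that the plan itself states, namely that the stimulation lowers contralesional M1 function. It needs no assumption about sample size. It does not make a useless classifier look accurate.

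The selection point is a cheap improvement. Its size, about 54% to 58% against a true 50%, holds only if the best of the three named techniques is picked on the evaluation folds, and only for the assumed patient and predictor numbers; the documents give neither for Study 3. A reader might go further and infer that the plan has no real validation, or that subsets would be screened on all patients before cross-validation, which would inflate accuracy much more. The plan describes no such screening, and its promise of separate data speaks against it.

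The predictor list and the handling of sham are matters for clarification only.

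**What to change.** 1. Reverse the labelling sentence in Section 2 so that it agrees with Section 3: deterioration after downregulation indicates a supportive role, improvement a detrimental one. Repeat this mapping in Study 3 and state which of the two a positive response means. The cost is wording only.
2. State that technique, tuning and subsets are chosen in an inner loop within the training data, and that only outer-loop performance is reported. The cost is slightly more computing and a less favourable reported accuracy.
3. List the Study 3 predictors, and exclude any measure used to form the label or taken after rTMS.
4. State how sham enters the response, given that Study 1 makes it the comparator. Subtracting sham is one option, with a trade-off. Assume change reliability 0.5, equal error in both sessions and no shift common to both. The chance of getting the sign of the response wrong is then arccos(√0.5)/π = 25% without subtraction and arccos(√(0.5/1.5))/π = 30% with it.

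None of these changes affects visits, patients or stimulation.

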#### 4.3. TMS data analysis:

Peak to peak MEP amplitudes will be measured off-line. Recordings with EMG background activity will be excluded from further analysis. Data analysis SICE, SRC, rIHI, aIHI, and mapping: Peak to peak MEP amplitudes will be measured off-line. Recordings with EMG background activity will be excluded from further analysis. For

the SRC, the mean MEP amplitudes at each stimulus intensity will be calculated. For SICE, rIHI and aIHI, mean MEP amplitudes elicited at different ISIs and CS intensities will be calculated as a percentage of the mean test MEP amplitude evoked by TS alone. CS intensities will be expressed as percentage of the subject's MT. For mapping, the area will be calculated as the number of stimulation sites that produce an MEP in of the trials. The center of gravity (CoG), an estimate of the center of the map, will be calculated for each target muscle (ECU or FCU) based on the weighted MEP amplitudes at each active location. Statistical analysis: We will use linear mixed models to quantify the effects of subject type (cortical stroke patient, subcortical stroke patient, healthy control) along with other, measure-specific factors (outlined below) on outcomes of interest. The analyses will incorporate models of within-subject correlations stemming from multiple measures on each subject. Hypothesis testing will be conducted on mean model parameters at a significance level  $\alpha = 0.05$ . Post-hoc analysis will be corrected for multiple comparisons. For SICE: A mixed model will assess the effect of subject type and stimulated hemisphere (ipsi- or contralesional for the stroke subjects, zero for the controls) along with repeated measure CS intensity (60%, 80% MT) on relative conditioned MEP amplitude. For rIHI: A mixed model will be used to determine the dependence of relative conditioned MEP amplitude on subject type along with the repeated measures inhibition (cl\_M1 on il\_M1 and il\_M1 on cl\_M1) and ISI (2ms, 10ms). For aIHI: We will perform a mixed model analysis to determine the dependence of relative conditioned MEP amplitude on subject type along with the repeated measures inhibition (as above), time after go signal (0ms, 300ms, 400ms, and 450ms), and target size (small, extra-large). For SRC: The effect of the repeated measure stimulus intensity on the average MEP

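### Study 3 sets no null reference, no uncertainty and no negative outcome for its classifiers, so the best of several techniques can look predictive by chance

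*Combined protocol and SAP*

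**What the plan says.** The Study 3 part of section 4.4 is the whole plan for this analysis, because section 6 only refers back to the individual study sections.

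- **Outcome.** The plan says "we will train (and test) a binary classifier to predict subjects' responses (positive or negative) to rTMS (down regulation and sham". Both post-stroke time points (month 1 and month 6) are covered. The expected split between positive and negative responses is not given.
- **Validation.** Iterative cross-validation, in which "different data are used to establish a predictive model and to evaluate its performance".
- **Measures.** "We will assess performance using standard measures of prediction accuracy such as sensitivity", followed by "specificity, positive predictive value, and negative predictive value". The list is introduced as examples.
- **Techniques.** "We will employ and compare multiple modeling techniques such as the Elastic Net, logistic classifier, and Bayes classifiers". They are compared with each other. No model without predictors is among them.
- **Conclusion.** "Developing and optimizing the classifiers will identify subsets of measures that have the greatest predictive power".

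The only significance level in the documents is the 0.05 in section 4.3, which has a different object: "Hypothesis testing will be conducted on mean model parameters at a significance level". It does not cover classifier performance. Section 5 gives 30 healthy subjects but no number of stroke patients, who are the units of Study 3.

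**The concern.** Some subset and some technique always rank first. A ranking therefore shows that something predicts only if the winner is set against what the same search would find when nothing predicts. The plan supplies no such reference, puts no uncertainty on any performance figure, and does not say what result would lead to the conclusion that no measure predicts the role of contralesional M1.

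Two features make the gap matter. PPV and NPV depend on the class mix, so they cannot be read without knowing what always predicting the larger class would give. And reporting the best of several techniques adds optimism that separating training from test data does not remove.

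Study 3 is the part of the project meant to say which patients have a supportive and which a detrimental contralesional M1. Section 3 expects the project's results to inform stimulation protocols tailored to that state. Sections 4.2 and 4.3 label certain other analyses exploratory, but Study 3 carries no such label. A subset named on chance-level performance could be carried into later trials.

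**Working it through.** The documents give no accuracy target, power or sample size for Study 3, so there is no figure of the plan's own to reproduce. The steps below show the size of the effect under stated assumptions.

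**1. Inputs.** From section 4.4: a binary outcome, held-out cross-validation, and three named technique families. Assumed: 20 to 60 stroke patients, 20 predictors that are pure noise, and a 50:50 split (70:30 in step 2).

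**2. What an uninformative rule scores.** If 70% of patients are in one class, always predicting that class gives sensitivity 100%, specificity 0%, PPV 70%, accuracy 70% and an undefined NPV. Guessing at the class frequencies gives sensitivity 70%, specificity 30%, PPV 70% and NPV 30%. In both cases sensitivity + specificity = 1, but PPV is 70% with no information at all.

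**3. Rough arithmetic for the best of three.** Treat held-out predictions as n independent coin tosses. For one classifier, the chance of at least 60% correct is P(X ≥ 0.6n), with X binomial(n, 0.5). For the best of three independent classifiers it is 1 − (1 − p)³.

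| n | 60% means | p, one classifier | best of three |
|---|---|---|---|
| 20 | 12 | 0.252 | 1 − 0.748³ = 58% |
| 30 | 18 | 0.181 | 1 − 0.819³ = 45% |
| 40 | 24 | 0.134 | 1 − 0.866³ = 35% |
| 60 | 36 | 0.0775 | 1 − 0.9225³ = 21% |

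This is only a guide. The three techniques share data, which lowers the figure. Cross-validated predictions are not independent, which widens the spread.

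**4. Null simulation.** This used 20 noise predictors, balanced classes, stratified 5-fold cross-validation with no subset search, and naive Bayes, ridge logistic and nearest centroid as stand-ins for the plan's families. The best of the three accuracies was recorded. Repeated runs gave these ranges for the share of null data sets in which the winner reached the threshold:

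| n | at least 60% | at least 65% |
|---|---|---|
| 20 | 49 to 52% | 34 to 36% |
| 30 | 38 to 44% | 17 to 20% |
| 40 | 34 to 40% | 17% |
| 60 | 23 to 28% | 8% |

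The winner's mean accuracy was about 0.55 to 0.57 (0.54 at the lowest in one run). The plan sets no 60% or 65% criterion. These thresholds only show how far chance can carry the winner.

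**5. What a reference would demand.** For one pre-specified classifier, the smallest number of correct held-out predictions that beats the majority-class rate at one-sided 0.05 (exact binomial, again treating predictions as independent) is:

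| n | 50% majority | 70% majority |
|---|---|---|
| 20 | 15 (75%) | 18 (90%) |
| 30 | 20 (66.7%) | 26 (86.7%) |
| 40 | 26 (65%) | 34 (85%) |
| 60 | 37 (61.7%) | 49 (81.7%) |

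A best-of-several search needs a reference that repeats the whole search, which these single-classifier values do not provide.

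**The case against.** The strongest reply is that the plan already contains much of the protection. Performance is judged on held-out data, which keeps any single fixed classifier near chance on average when nothing predicts. Sensitivity and specificity do not depend on class mix, and their sum is 1 for an uninformative rule. The majority-class rule with PPV 70% is exposed at once by its specificity of 0%. Elastic Net can select no predictors. All of this stands. It means that a careful reader could notice a null result. It does not mean that the plan requires anyone to look, gives the uncertainty needed to judge a sum slightly above 1, or allows for the choice of the best technique.

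Four stronger readings are tempting, and the documents do not support them.

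- **That these four measures are the only ones.** The list is introduced as examples, so AUC or balanced accuracy is not excluded.
- **That the plan cannot return a negative answer, or that chance-level results will be reported as biomarkers.** The closing sentence states an aim and is not a decision rule. What is missing is a defined condition for calling the result negative.
- **That noise would routinely look strongly predictive.** If the best of 36 subset-and-classifier combinations is chosen and judged on the same folds, noise winners average 0.63 to 0.72 balanced accuracy at 50:50 (12 noise predictors). That figure requires selection outside the training data. The plan does not say whether selection is nested, so it belongs to a different question and is not relied on here.
- **That with a 70:30 split, frequent accuracies of 65% or more show a problem.** 65% is below the 70% obtained by always predicting the larger class, so it shows nothing.

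The simulation also uses stand-ins, omits Elastic Net, and rests on assumed inputs. Its percentages are indicative.

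**Conclusion.** The concern holds in a limited form. Study 3 specifies no null reference and no uncertainty for classifier performance, and no condition under which no biomarker is claimed, while its conclusion is worded without condition. Clean cross-validation does not close the gap, because the winner among several techniques is optimistic. The optimism is modest on average, about 5 to 7 percentage points over 50%. It is erratic in small samples: 60% accuracy is reached by chance in roughly half of data sets at 20 patients and roughly a quarter at 60. These sizes rest on an assumed patient number, predictor count and class split, and on three stand-in classifiers. The finding that no reference is set does not depend on those assumptions.

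The interpretation of Study 3 is affected. The mixed-model analyses are not. This is an inexpensive improvement that should be made, ideally before outcomes are examined.

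**What to change.** Amend the Study 3 text in section 4.4 as follows.

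1. Make cross-validated AUC the headline measure, with a bootstrap interval that resamples patients. Balanced accuracy may be reported as well, but it depends on the cut-off, as sensitivity and specificity do.
2. Report the result of always predicting the larger class beside the four named measures, together with the observed class split.
3. Add a permutation test that permutes labels by patient, so that a patient's 1-month and 6-month records stay together. Each permutation should rerun the whole pipeline: all techniques, tuning and subset selection.
4. State that, if performance does not exceed the permutation reference, any selected subset will be described as not shown to predict the role of contralesional M1.

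Other designs are defensible for model development. An interval alone could serve if it covered the selection step, but the permutation reference deals directly with choosing the best of several.

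The cost is analysis-plan wording and computing time. No visit, measurement or patient changes. The real downside is that Study 3 may end with no biomarker identified.
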